9. SAFETY EVALUATION

9.1. Demographic and Other Baseline Characteristics

Subject demographic variables (i.e., age, sex, race, and ethnicity) will be summarized by treatment and overall using descriptive statistics for age, and using number and percentage of subjects for sex, race, and ethnicity (Table 14). Age at Study Day 1 is calculated in years at the first dosing date of study product and will be rounded down to an integer. Age group (<40; 40-64; 65 or older) will be summarized by using summary statistics for categorical variables. If a subject did not receive study product after enrollment, the subject's age will be calculated from the date of randomization unless stated otherwise in a stage-specific appendix.

A demographic listing, including the informed consent date, will be provided Listing 5.

Baseline characteristics include body weight (in kg), height (in cm), body mass index (BMI; in kg/m²), duration of symptoms prior to enrollment, steroid use, baseline viral measures and ordinal score. These baseline characteristics will be summarized by the treatment group and overall using descriptive statistics for continuous variables and using number and percentage of subjects for categorical variables (Table 15). No formal statistical testing is planned.

A listing of baseline characteristics will be provided (Listing 5).

9.1.1. Prior and Concurrent Medical Conditions

Focused medical history is obtained at the screening visit that includes the following:

- Day of onset of COVID-19 signs and symptoms.
- Prior enrollment in ACTIV-5/BET.
- History of vaccinations within 4 weeks prior to screening, including SARS-CoV-2 vaccination.
 - Exclusionary vaccine history includes any live vaccine (that is, live attenuated) within 4 weeks prior to screening
- History of chronic medical conditions including chronic oxygen requirement prior to onset of COVID-19.
- History of medication allergies.
- Medications and therapies for this current illness taken in the 7 days prior to Study Day 1.
- Whether subject is participating in another clinical trial or plan to enroll in another clinical trial in the next 30 days.

Medical history is limited to the following conditions: asthma, cancer, cardiac vascular disease, chronic kidney disease, chronic liver disease, chronic oxygen requirement, chronic respiratory disease, coagulopathy, congestive heart failure, coronary artery disease, current nicotine consumption, diabetes type I and II, hypertension, immune deficiency, and obesity. Summaries of subjects' medical history will be presented by treatment group and overall (Table 14, Table 15).

A listing of medical history will be provided by subject number. Additional medical history other than the diagnoses listed above will be included in the listing (Listing 6).

9.1.2. Prior and Concomitant Medications

Concomitant medications will be coded to the Anatomical Therapeutic Classification using the WHODrug Dictionary. The use of prior and concomitant medications taken during the study will be recorded on the CRFs.

Prior medications are defined as any medications begun and stopped before a subject took the first dose of study product. If a partial stop date is entered, the month and year (if day is missing) or year (if day and month are missing) of the stop date are prior to the first dosing date will be considered prior (See [Table 8](#)).

Concomitant medications are defined as medications taken while a subject took study product. Therefore, any medications started prior to or during the first dosing date of study product and continued after the first dosing date or started after the first dosing date will be considered concomitant medications. If a partial start date is entered, any medication with the month and year (if day is missing) or year (if day and month are missing) after the date of first study product administration will be included in the concomitant medication summary. Medications with completely missing start and stop dates will be included in the concomitant medication summary ([Table 8](#)).

Prior and concomitant medications reported on the concomitant medication form will be summarized separately WHO Drug Level 1 and 2 Codes, actual baseline ordinal score, and treatment group using the number and percentage of subjects for each treatment, actual baseline ordinal score, and overall ([Table 84](#), [Table 85](#)). Concomitant COVID-19 treatments are reported in [Table 86](#) while steroids used for indications other than COVID-19 are reported in [Table 87](#). A subject reporting the same medication more than once will be counted only once when calculating the number and percentage of subjects who received that medication. The summary will be ordered alphabetically by WHO Drug level 1 code then by WHO Drug level 2 code in order of descending overall frequency within each WHO Drug level code. For drugs with the same frequency, sorting will be done alphabetically.

Summaries of prior and concomitant medications will be based on the Safety population and individual subject listing of all prior and concomitant medications including those reported on the SAE form is provided in [Listing 9](#), [Listing 10](#) for steroids, and [Listing 11](#) for other medication of interest.

9.2. Measurements of Treatment Compliance

Section 7 provides the descriptions of summaries of key treatment compliance milestones/variables. Individual subject listings will be presented for all subjects who discontinued dosing ([Listing 1](#)). Individual subject listings will be presented for all subjects who missed, halted or slowed any dose ([Listing 12](#)).

9.3. Adverse Events

All safety analyses will be summarized and performed on the Safety population by treatment and ordinal score, as appropriate.

Clinical and laboratory adverse events (AEs) will be coded using the version 23.0 of MedDRA. System organ class (SOC) and preferred term (PT) will be provided in the AE dataset.

AEs are graded by the investigator as Grade 2 (moderate), Grade 3 (severe), Grade 4 (severe/potentially life-threatening), or Grade 5 (fatal/death) according to the NIAID Division of AIDS (DAIDS) Table for Grading the Severity of Adult and Pediatric Adverse Events, Corrected Version 2.1 [5]. The severity grade of events for which the investigator did not record severity will be categorized as “missing” for tabular summaries and data listings. The missing category will be listed last in summary presentation.

The relationship of an adverse event to the component of the investigational product should be assessed using clinical judgment by the investigator, describing the event as either unrelated or related. Events for which the investigator did not record relationship to study product will be considered related to study product for summary purposes. However, data listings will show relationship as missing. Relationship to COVID-19 and other medical conditions is also collected and will be reported in data listings.

Treatment-emergent adverse events (TEAEs) are defined as any AE with an onset date on or after the study product start date.

If the onset date of the AE is incomplete and the AE stop date is not prior to the first dosing date of study product, then the month and year (or year alone if month is not recorded) of onset determine whether an AE is treatment emergent. The event is considered treatment emergent if the AE onset is the same as or after the month and year (or year) of the first dosing date of study product.

An AE with completely missing onset and stop dates, or with the onset date missing and a stop date later than the first dosing date of study product, will be considered to be treatment emergent. In addition, an AE with the onset date missing and incomplete stop date with the same or later month and year (or year alone if month is not recorded) as the first dosing date of study product will be considered treatment emergent. For additional details on imputation of partial or missing dates, see [Table 8](#).

For the calculation of incidence of TEAEs each subject will only be counted once per category (Any TEAEs, Any SOC, Any PT within SOC) and any repetitions of TEAEs within a subject will be ignored; the denominator will be the number of subjects in the Safety population.

An overall summary of TEAEs by treatment, actual baseline ordinal score, severity, and relatedness of TEAEs will be presented in [Table 46](#) and will include subjects with at least one:

- TEAE
- Grade ≥ 3 TEAE
- TEAE related to study treatment
- Grade ≥ 3 TEAE related to study treatment
- Treatment-emergent SAE
- Treatment-emergent SAE related to study treatment
- TEAE leading to early termination of study product
- TEAE leading to study discontinuation
- TEAE leading to death.

The following summaries for TEAEs will be presented by MedDRA system organ class, preferred term, severity and relatedness (when applicable) of TEAE, ordinal score and treatment:

- Subject listing of non-serious AEs ([Listing 15](#));
- Bar chart of non-serious related AEs by severity and MedDRA system organ class (beginning at [Figure 23](#) and continuing through [Figure 30](#));

The proportion of subjects reporting at least one TEAE will be summarized by MedDRA system organ class and preferred term for each treatment ([Table 47](#)), by baseline ordinal score ([Table 48](#)), by baseline steroid use ([Table 49](#)), by baseline use of Emerging COVID-19 treatments ([Table 50](#)), and by duration of symptoms prior to enrollment ([Table 51](#)). Denominators for percentages are the number of subjects in the Safety population.

Similarly, the proportion of subjects reporting at least one treatment-emergent SAE will be summarized by MedDRA system organ class and preferred term for each treatment, ordinal score and overall (Table 52, Table 53).

Separate listings of non-serious TEAEs, all TEAEs, related TEAEs, treatment-emergent SAEs, and TEAEs leading to early termination of study product, TEAEs leading to study discontinuation or death will be presented (beginning at Listing 15 and continuing through Listing 21).

9.4. Deaths, Serious Adverse Events and other Significant Adverse Events

The time to death up to and including Day 60 will be defined as the elapsed time (in days) from Study Day 1 to date of death. Any subjects whose last assessment is prior to death will be censored at the date of their last observed assessment. For the sensitivity analysis of this endpoint, subjects discharged to a location other than LTAC, hospice care, or other hospital will be considered non-events and censored at Day 60. For both analyses, subjects who complete follow-up will be censored at Day 60. Deaths that occur after Day 60 will be censored at Day 60. The Kaplan-Meier estimates of mortality rates along with corresponding 80% CI and 95% CI will be presented by treatment group and baseline ordinal score. Difference in Kaplan-Meier estimates of mortality rates between treatment arms along with corresponding 80% CI, 95% CI will be presented. Additionally, hazard ratios along with corresponding 80% CI, 95% CI and score test p-value calculated from the Cox proportional hazard model adjusted from baseline ordinal score and baseline steroid use will be presented (Table 54).

This analysis will be repeated for deaths through Day 15 and deaths through Day 29 and results will be reported in Table 54. Restricted mean mortality time estimates will be provided for each treatment group and actual baseline ordinal score stratum as well as the difference in restricted mean mortality time between treatment groups within each of the baseline ordinal score strata (Table 55).

Differences in time-to-event endpoints by treatment will be summarized with Kaplan-Meier curves (Figure 12, Figure 13, Figure 14). Analyses of mortality will be performed on the Safety population at risk.

A safety composite endpoint will be defined as the occurrence of at least one of the following up to and including Study Day 60:

1. Death
2. Treatment-emergent SAE
3. Grade 3 or 4 TEAE

The time to this composite endpoint will be defined as the elapsed time (in days) from Study Day 1 to the earliest date of any of the events. Any subjects whose last assessment in the study is prior to experiencing any of the events will be censored at the day of their last observed assessment. Subjects who complete follow-up but do not experience any of the events will be censored at the expected date of their Study Day 60 visit.

Rates death, SAE, and Grade ≥ 3 TEAEs occurrence up to and including expected date of the Study Day 60 visit will be presented for each treatment arm. Further, the composite endpoint of the occurrence of death, treatment-emergent SAE, or Grade 3 or 4 TEAE will be analyzed as a time-to-event outcome. A table will present Kaplan-Meier estimates of the event rates along with corresponding 80%, 95% confidence intervals for each treatment. Difference in event rates along with corresponding 80%, 95% confidence intervals will also be presented. Hazard ratio estimates and score test p-value from the Cox model will also be presented (Table 56). Differences in time-to-event endpoints by treatment will also be summarized with Kaplan-Meier curves (Figure 18).

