6.5. Missing Data

6.5.1. General Guidelines Regarding Handling of Missing Data

All attempts will be made to collect all data per the protocol. Efforts to minimize loss-to-follow-up will be considerable. Chart review will be performed for lost-to-follow-up subjects to obtain data related to the subjects' clinical status, oxygen use, or death status after discharge. However, small amounts of missing data may occur. In order to conduct mITT and ITT analyses for primary and secondary outcomes, missing data will be imputed in the manners described below in [Table 7](#). Prior to applying the imputation rules described in [Table 7](#), an endpoint review committee (ERC) may meet to adjudicate the primary endpoint and the key secondary endpoints for each study stage, such as Day 8 ordinal scores for subjects discharged to hospice, another hospital, or long-term care facilities. Any ERC reviews will be performed prior to database lock and all committee members will be blinded to treatment assignments. If an ERC is used, an ERC charter will be prepared prior to any reviews.

For the primary analysis of ordinal score at Day 8, the following imputations will be performed prior to multiple imputation:

- If a subject is discharged from the hospital to another location other than LTAC, hospice care or other hospital, has intermittent missing ordinal score and reported an ordinal score of 1 or 2 after the missing score then:
 - The intermittent missing ordinal score is imputed as 1 if the scores reported before and after the missing value are both 1 and no change in oxygen use or hospitalization status after discharge to a location other than hospice, long term acute care or other hospital.
 - The intermittent missing ordinal score is imputed as 2 after discharge to a location other than hospice, long term acute care or other hospital if the subject doesn't fall into the category above and subject is not hospitalized at the time point.
- LOCF will be used for remaining intermittent missingness of ordinal scores for the next planned assessment.
- All missing scores after death will be assigned an ordinal score of 8.
- Subjects that terminated from the study with known discharge to a location other than hospice, LTAC or other hospital at their last assessment will be assigned a score of 2 for all timepoints after last assessment.

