11. Proportion of subjects alive and without respiratory failure at Study Day 29;	Primary	
 Use the complete data for ordinal score to define survival without respiratory failure. Subjects will be considered events at Day 29 if they are dead or are on invasive mechanical ventilation/ECMO anytime between Day 26 and Day 32 (Window for Day 29) regardless of their baseline ordinal score. All subjects who died before Day 26 (beginning of Day 29 visit window) will be considered events. All subjects who died after Day 32 or those who were not on invasive mechanical ventilation/ECMO between Day 26 and Day 32 will be considered non-events.
12. Time (days) to ventilation or death up to and including Day 29;	Primary	
 Use the complete data for ordinal score to define survival without respiratory failure. All subjects whose last assessment in the study is before Day 26 and before progression to mechanical ventilation or death will be considered non-events and censored at the date of their last observed assessment. Subjects who complete follow-up without mechanical ventilation or death will be censored at the expected study Day 29. Subjects whose last assessment in the study is before Day 29 but within window for Day 29 (i.e., Day 26, 27, 28) and before experiencing death or progression to mechanical ventilation will be considered non-events regardless of their discharge status at Day 29.
	Primary with Sensitivity Imputation	
 Use the complete data for ordinal score to define survival without respiratory failure. Subjects whose last assessment in the study is before Day 26 and were discharged to a location other than LTAC, hospice care or other hospital, or progressed to mechanical ventilation or death after Day 29 will be considered non-events and censored at Day 29. Subjects whose last assessment in the study is before Day 26 and before progression to mechanical ventilation or death and without being discharged to a location other than LTAC, hospice care or other hospital at their last assessment will be considered non-events and censored at the date of their last observed assessment. Subjects who complete follow-up without mechanical ventilation or death will be censored at the expected study Day 29.

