13. Days of hospitalization from date of admission by Study Day 29.	Primary	
 If a subject is discharged and no further hospitalization data are available, consider the subject as not readmitted, no additional imputed days will be added. If a subject dies while hospitalized, the number of days of hospitalization will be imputed as the number of days between the date of admission and the expected date of subject's Study Day 29 visit+1.
	Subgroup	
 Use complete data for ordinal score to define this endpoint.

Endpoint	Analysis	Imputation Method
Other Secondary Endpoints: Safety		
1. Values of CRP, ferritin, D-dimer, LDH, and fibrinogen on Study Day 1: Study Days 3, 5, 8, 11,15 and 29	Primary	
 If results are not available for any visit day(s) but are available for visits before or after that visit, the average of the two nearest visits will be imputed for all missing visits between them. If a subject dies or is otherwise terminated early from the study, their last available observation will be carried forward. If baseline is missing, another pre-treatment dose will be used, or the earliest post treatment dose will be used.
2. 14-day Mortality	Primary	
 Subjects whose last assessment in the study is before Day 13 (beginning of Day 29 window) and before death will be considered not dead and censored at the date of their last observed assessment. Subjects who complete follow-up will be censored at Day 15. Deaths that occur after Day 15 will be censored at Day 15.
	Primary with Sensitivity Imputation	
 Subjects whose last assessment in the study is before Day 13 (beginning of Day 15 window) and were discharged to a location other than LTAC, hospice care or other hospital, or subjects died after Day 15 will be considered non-events and censored at Day 15. Subjects whose last assessment in the study is before Day 13 (beginning of Day 15 window) and before death and without being discharged to a location other than LTAC, hospice care or other hospital at their last assessment will be considered non-events and censored at the date of their last observed assessment. Subjects who complete follow-up will be censored at Day 15.

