3. 28-day Mortality	Primary	
 Subjects whose last assessment in the study is before Day 26 (beginning of Day 29 window) and before death will be considered not dead and censored at the date of their last observed assessment. Subjects who complete follow-up will be censored at Day 29. Deaths that occur after Day 29 will be censored at Day 29.
	Primary with Sensitivity Imputation	
 Subjects whose last assessment in the study is before Day 26 (beginning of Day 29 window) and were discharged to a location other than LTAC, hospice care or other hospital, or subjects died after Day 29 will be considered non-events and censored at Day 29. Subjects whose last assessment in the study is before Day 26 (beginning of Day 29 window) and before death and without being discharged to a location other than LTAC, hospice care or other hospital at their last assessment will be considered non-events and censored at the date of their last observed assessment. Subjects who complete follow-up will be censored at Day 29.
4. 59-day Mortality	Primary	
 Subjects whose last assessment in the study is before Day 57 (beginning of Day 60 window) and before death will be considered not dead and censored at the date of their last observed assessment. Subjects who complete follow-up will be censored at Day 60. Deaths that occur after Day 60 will be censored at Day 60.
	Primary with Sensitivity Imputation	
 Subjects whose last assessment in the study is before Day 57 (beginning of Day 60 window) and were discharged to a location other than LTAC, hospice care or other hospital, or subjects died after Day 60 will be considered non-events and censored at Day 60. Subjects whose last assessment in the study is before Day 57 (beginning of Day 60 window) and before death and without being discharged to a location other than LTAC, hospice care or other hospital at their last assessment will be considered non-events and censored at the date of their last observed assessment. Subjects who complete follow-up will be censored at Day 60.

Endpoint	Analysis	Imputation Method

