The time to mechanical ventilation or death up to and including Day 29 will be defined as the elapsed time (in days) from Study Day 1 to date of mechanical ventilation or death. Any subjects whose last assessment is prior to obtaining the event and prior to Day 26 (beginning of Day 29 window) will be censored at the date of their last observed assessment. For the sensitivity analysis of this endpoint, subjects whose last assessment is

prior to obtaining the event and who were discharged to a location other than LTAC, hospice care, or other hospital will be considered recovered and censored at Day 29. For both primary and sensitivity analysis of this endpoint, subjects who complete follow-up will be censored Day 29. Events that occur after Day 29 will be censored at Day 29. A table will present median time to event along with corresponding 95% and 80% confidence intervals for each treatment along with the hazard ratio estimate and score test p-value from a Cox-proportional hazard model (Table 42). The Cox model will include as covariates baseline ordinal score, baseline CRP value, continuous age, and baseline dexamethasone use. Differences in time-to-event endpoints by treatment will be summarized with Kaplan-Meier curves (Figure 11). Analyses will be performed on the mITT population for those subjects who at baseline have an ordinal score of 5 or 6, CRP<150 mg/L, and age<85 years and results will be reported in Table 42. This analysis will be repeated for all subjects in the mITT population and results will be reported in Table 43.

Refer to Table 6 for a list of covariates and subgroup analyses for this endpoint. Refer to Table 7 for imputation methods to be applied to this endpoint.

Hospitalization

Duration (in days) of hospitalization will be defined as the number of days subject is hospitalized for COVID-19-related reasons starting from the date of randomization. It will be calculated as the total number of days hospitalized, including readmissions for COVID-19-related reasons. It will also be calculated as the total number of days hospitalized, including any readmissions regardless of cause. See Section 6.5 for the plan for handling subjects who do not have data through Day 29 or die prior to Day 29.

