		Treatment B (N=X)	X	x.x	x.xx	x.x, x.x	x.xxx								
	7	Treatment A (N=X)	X	x.x	x.x	x.x, x.x	x.xxx	x.x	x.x, x.x	x.x, x.x	x.x	x.x, x.x	x.x, x.x	0.xxx	

Analysis Type	Baseline Ordinal Score	Treatment Group	Number of Deaths		Mortality Rate (CI) ^c			Difference in Mortality Rates at the Specified Time Point ^d			HR ^e			P-value ^f
			n	%	Estimate	80% CI	95% CI	Estimate	80% CI	95% CI	Estimate	80% CI	95% CI	
		Treatment B (N=X)	X	x.x	x.xx	x.x, x.x	x.xxx							
	Any BOS	Treatment A (N=X)	X	x.x	x.x	x.x, x.x	x.xxx	x.x	x.x, x.x	x.x, x.x	x.x	x.x, x.x	x.x, x.x	0.xxx
		Treatment B (N=X)	X	x.x	x.xx	x.x, x.x	x.xxx							

CI= Confidence Intervals. N=Number of subjects in the Safety population. n= Number of unique subjects that satisfies the row criteria.

^a For the primary endpoint, all subjects whose last assessment was before the corresponding timepoint (Day 15 Visit, Day 29 Visit, Day 60 Visit) and were missing the event were censored at the date of last assessment.

^b Primary with Sensitivity Imputation: Same analysis as the initial model but subjects missing event and whose last assessment is before the corresponding timepoint (Day 15 Visit, Day 29 Visit, Day 60 Visit) are non-events for good discharges and censored at Day 15, Day 29, Day 60 respectively or at last assessment for subjects still hospitalized or discharged to LTAC, hospice care, or other hospital.

^c Mortality Rates are the Kaplan-Meier estimates.

^d Difference in mortality rates (80%, 95% CI) obtained from Kaplan Meier.

^e HR is the hazard ratio from the Cox Proportional Hazard Model adjusted for baseline ordinal score and baseline steroid use.

^f P-value is based on the Cox adjusted model.

Table 55: Time to Death through Day 15, 29, or 60 by Treatment Group: Restricted Mean Survival Time Analysis — Safety Population

Study Day	Treatment Group	Actual Baseline Ordinal Score	n	Restricted Mean Mortality Time (Days)		Difference	
				Estimate	95% CI	Estimate	95% CI
Day 15	Treatment A (N=X)	5	x	x.x	x.x, x.x	x.xx	x.xx, x.xx
	Treatment B (N=X)		x	x.x	x.x, x.x		
	Treatment A (N=X)	6	x	x.x	x.x, x.x	x.xx	x.xx, x.xx
	Treatment B (N=X)		x	x.x	x.x, x.x		
	Treatment A (N=X)	7	x	x.x	x.x, x.x	x.xx	x.xx, x.xx
	Treatment B (N=X)		x	x.x	x.x, x.x		
	Treatment A (N=X)	Any BOS	x	x.x	x.x, x.x	x.xx	x.xx, x.xx
	Treatment B (N=X)		x	x.x	x.x, x.x		

Repeat for Day 29 and Day 60

N= Number of subjects in the specified treatment group, actual baseline ordinal score, and analysis population.

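### In the sensitivity analyses, SAP Section 9.4 and five Table 7 rows make home-discharged subjects non-events without requiring that they be event-free, contradicting Section 8.2.2 and the footnotes to Tables 42 and 54

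*SAP*

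**What the plan says.** Below, home discharge means discharge anywhere other than long-term acute care, hospice or another hospital.

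**Text without an event-free condition**

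- SAP Section 9.4, sensitivity analysis of time to death to Day 60, repeated for Days 15 and 29: "subjects discharged to a location other than LTAC, hospice care, or other hospital will be considered non-events and censored at Day 60". It sets no limit on the date of the last assessment.
- SAP Table 7 (Section 6.5.1), sensitivity rows for 14-, 28- and 59-day mortality and time to death by Day 29. The home-discharge bullet asks only for a last assessment before the visit window and a home discharge. The 14-day row reads "beginning of Day 15 window) and were discharged to a location other than LTAC, hospice care or other hospital, or subjects died after Day 15"; the 28-day row ends "or subjects died after Day 29 will be considered non-events and censored at Day 29".
- SAP Table 7, efficacy row 12 (time to ventilation or death), sensitivity row: same structure, ending "or progressed to mechanical ventilation or death after Day 29 will be considered non-events and censored at Day 29".

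**Text with the condition**

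- Section 8.2.2, time to ventilation or death: the sensitivity rule covers subjects whose last assessment is "prior to obtaining the event and who were discharged to a location other than LTAC, hospice care, or other hospital".
- Table 54 footnote b, mortality: "Same analysis as the initial model but subjects missing event and whose last assessment is before the corresponding timepoint". Table 42 footnote b has the same restriction for ventilation or death.
- Table 7, sensitivity row for survival without respiratory failure: it requires that the last assessment precede death or ventilation.
- In the affected Table 7 rows, the companion bullet for subjects not discharged home also carries the condition.

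**Primary mortality rule, Section 9.4:** "Any subjects whose last assessment is prior to death will be censored at the date of their last observed assessment".

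**The concern.** A sensitivity analysis of this kind should ask what happens if subjects lost after going home are assumed to have stayed well. It should change only the handling of unknown outcomes. As worded in Section 9.4 and the five Table 7 rows, it also reaches subjects whose outcome is known.

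Such subjects are foreseeable. Section 4.5 takes deaths from the SAE form, and Section 6.5.1 says "Chart review will be performed for lost-to-follow-up subjects to obtain data", naming death status after discharge among the items sought. The plan therefore expects to learn of some deaths after the last visit. Home discharge is itself a post-randomization outcome, so recoding on it need not be balanced between arms.

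Two programmers could follow different parts of the SAP and produce different sensitivity rows in Table 54 or Table 42. Section 6.5.1 would also score a post-death visit as 8 on the ordinal scale, while the literal mortality sensitivity rule called the same subject a non-event.

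**Working it through.** The SAP states no figure on this point. The check is to trace example subjects through each rule as written, and then to size one recoded death.

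**Traces** (hypothetical subjects; rules and windows from the SAP)

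| Subject | Literal sensitivity rule | Restricted rule |
|---|---|---|
| A: home Day 6, last visit Day 15, death Day 20 on the SAE form | Table 7, 28-day mortality: 15 < 26 and home, so non-event, censored Day 29. Section 9.4: home, so non-event, censored Day 60 | Table 54 footnote b: the event is not missing, so event on Day 20 |
| B: intubated Day 4, home Day 18, last visit Day 22 | Table 7 row 12: 22 < 26 and home, so non-event, censored Day 29 | Section 8.2.2 and Table 42 footnote b: event on Day 4 |
| C: intubated Day 4, home Day 18, completes Day 29 | Table 7 row 12: 29 is not before 26, so the bullet does not apply; event | Event |

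A and B show the contradiction. C marks its limit: row 12 loses an intubation only if the last assessment falls before Day 26.

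Table 7's 59-day row applies only when the last assessment is before Day 57. Section 9.4 has no such limit, so read literally it covers every home-discharged subject, including those followed into the Day 60 window.

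**Size of one recoded death.** With 100 subjects per arm (SAP Section 5), 1/100 = 1 percentage point of that arm's mortality. This uses the crude proportion, which equals the Kaplan-Meier estimate when nobody is censored earlier.

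**Illustration.** Assumed, not in the documents: 12 deaths per 100 in each arm, of which 0 to 4 per arm follow home discharge and are recoded. Approximate hazard ratio = ln(1 − p_active) / ln(1 − p_placebo).

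| Recoded, active / placebo | Reported mortality | Approximate HR |
|---|---|---|
| 0 / 0 | 12% vs 12% | 1.00 |
| 1 / 1 | 11% vs 11% | 1.00 |
| 2 / 0 | 10% vs 12% | 0.1054 / 0.1278 = 0.82 |
| 4 / 0 | 8% vs 12% | 0.0834 / 0.1278 = 0.65 |
| 4 / 4 | 8% vs 8% | 1.00 |

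Equal recoding understates mortality in both arms but leaves the comparison unchanged. Only unequal recoding creates an apparent difference.

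**The case against.** The best defence is that no one would program the literal reading.

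- Section 6.5.1 introduces Table 7 as a way of handling missing data, and a recorded death is not missing. The same section says time-to-event endpoints use observed scores together with discharge and death information.
- The disputed bullets name deaths or progression after the cutoff as non-events. That clause would be largely redundant if earlier events in home-discharged subjects were non-events too.
- In Section 9.4 the sensitivity sentence follows directly on the sentence about subjects last seen before death, so it can be read as changing only where those subjects are censored.
- Table 54 prints the number of deaths in both the primary and the sensitivity rows, so a lost death would be visible.

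Much of this stands as evidence of intent, and it is why the point is a contradiction rather than a settled deletion of events. It does not cure the wording. The condition is stated in the companion bullets and in the survival-without-respiratory-failure row but left out of the five rows, so a reader can take the omission as deliberate. A mismatch in Table 54 would be seen only after the analysis had been run.

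Stronger readings are tempting, but the documents do not support them:

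- *That observed events are removed from the main mortality and ventilation-or-death analyses.* The recoding appears only in sensitivity rules.
- *That the primary rule censors every death after the last visit.* Read literally, "Any subjects whose last assessment is prior to death will be censored at the date of their last observed assessment" could do so for a death known from the SAE form. But Section 9.4 measures time to the date of death, and Table 54 footnote a limits this censoring to subjects missing the event. The sentence is ambiguous, no more.
- *That an arm which sends ventilated patients home sooner is systematically favoured.* Subject C shows that early loss to follow-up is also needed, and the documents give no rate for it.

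**Conclusion.** The point holds as an internal contradiction confined to sensitivity analyses. Section 9.4, Table 7 safety rows 2 to 5 and Table 7 efficacy row 12 omit the event-free condition that Section 8.2.2 and the footnotes to Tables 42 and 54 apply to the same analyses. Section 9.4 also omits Table 7's limit on the date of the last assessment. Followed literally, these rules turn known events before the cutoff into non-events.

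The size is about 1 percentage point of an arm's mortality per recoded death at 100 per arm. How many there would be, and whether they would differ by arm, cannot be derived from the documents; the hazard ratios above rest on assumed counts. For time to sustained recovery, Section 8.2.1 expects few subjects to worsen after discharge, which suggests small numbers.

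This should be fixed, but it does not threaten the trial's main conclusion: the decision to call an intervention promising rests on the Day 8 ordinal score, which these rules do not touch.

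**What to change.** In Section 9.4, Table 7 safety rows 2 to 5 and Table 7 efficacy row 12, state the order of operations:

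1. Any documented death dated on or before the cutoff (for row 12, any documented ventilation or death) is an event on its date, whether learned from the SAE form, a status assessment or chart review.
2. Only subjects with no recorded event and a last assessment before the visit window are treated as incompletely followed. They are censored at the last assessment in the primary analysis. In the sensitivity analysis they are censored at the cutoff day if discharged home, and otherwise at the last assessment.

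In Section 9.4 this also supplies the missing last-assessment limit and removes the ambiguity in the primary sentence. The same edit can correct the 14-day primary row of Table 7, which labels Day 13 as the start of the Day 29 window.

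The cost is SAP wording in one section and five table rows, using a rule the SAP already states elsewhere. No new data are needed. It should be settled before unblinding, so that the choice of reading cannot depend on results.
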